**Table 4. Summary of Efficacy Variables and Corresponding Analyses for Efficacy Analysis in Period 1 (Continued)**

Efficacy Variables	Analysis Method
Additional Variables (Summarized at all Visits up to Week 12) (continued)	

Continuous Endpoints:
 
 
• Change from baseline in individual ACR components
 
• Change from baseline in DAS28 (CRP) and DAS28 (ESR)
 
• Change from baseline in CDAI and SDAI
 
• Change from baseline in morning stiffness (severity and duration)
 
• Change from baseline in EQ-5D-5L
 
• Change from baseline in FACIT-F
 
• Change from baseline in RA-WIS
 
• Change from baseline in SF-36
 
	
 
• LS mean and 95% CI within each treatment group and LS mean, 95% CI and p-values between each upadacitinib dose group and the combined placebo group using MMRM model with fixed effects of treatment, visit and treatment-by-visit interaction, prior bDMARD use and baseline value as covariate. Only nominal p-value will be provided.
 
• Analysis Set: FAS
 

- a. US/FDA regulatory purposes.  
b. EU/EMA regulatory purposes.

### 9.3 Long-Term Efficacy Analysis

Assessments to evaluate long-term efficacy will be analyzed for the following measures at Week 1, 2, 4, 8, 12, 16, 20, 24, 36, 48, every 12 weeks through Week 240, and Week 260.

- ACR20/50/70 response rates;
- Change from baseline in individual ACR components;
- Change from baseline in DAS28 (CRP);
- Change from baseline in DAS28 (ESR);
- Change from baseline in morning stiffness (severity and duration);
- Proportion of subjects achieving LDA and proportion of subjects achieving CR based on DAS28 (CRP), DAS28 (ESR), SDAI, and CDAI criteria;
- Proportion of subjects with no concomitant corticosteroid use (among subjects with corticosteroid use at baseline).

Assessments to evaluate long-term efficacy will be analyzed for the following measures at Week 4, 12, 24, 48:

- Change from baseline in EQ-5D-5L;
- Change from baseline in FACIT-F;
- Change from baseline in RA-WIS;
- Change from baseline in SF-36.

Analyses will be based on As Observed (AO) data. Descriptive statistics will be provided for each randomized treatment group sequence as defined in Section 9.1.1. These include the number of observations, mean, standard deviation, and 95% CI for continuous endpoints; and frequencies and percentages with 95% CI using normal approximation for binary endpoints. In addition, longitudinal analysis will be performed using MMRM or GLMM as described in Section 9.1.2 for all endpoints except proportion of subjects with no concomitant corticosteroid use. Point estimates and 95% CI from the model will be provided for each treatment group sequence. Plot for each randomized treatment group sequence over time will be provided.

Table 5 below provides the overview of the long-term efficacy analyses to be performed on different endpoints.

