### **Period 2 (Long-Term Extension Period [248 Weeks])**

Period 2 will begin at the Week 12 visit after all assessments have been completed. During Period 2, subjects will have a study visit at Weeks 16, 20, 24, 36, 48, and every 12 weeks through Week 240 and Week 260/PD. A  $\pm 7$  day window is permitted

aroundscheduled study visits. At Week 24, if a subject fails to meet LDA criterion (LDA defined as  $CDAI \leq 10$ ) investigator should adjust the subject's background RA therapies.

Starting at Week 24 and thereafter, at least 20% improvement in BOTH TJC AND SJC is required to remain on study drug. Anyone who does not fulfill this criterion at 2 consecutive visits (starting at Week 24) must be discontinued from study drug.

Starting with Amendment 6, all subjects will receive open-label upadacitinib 15 mg QD, including those currently on upadacitinib 30 mg QD.

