**As Observed (AO)**

The AO analysis will not impute values for missing evaluations. Regardless of treatment switching or premature discontinuation of study drug, all observed data will be used in the analysis. The AO analysis will be applied to long-term efficacy analysis.

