**MMRM and Generalized Linear Mixed Model (GLMM) for Long-Term Analysis**

The repeated measure analysis will be conducted using mixed model including As Observed measurements at all visits. MMRM will be used for continuous endpoints and GLMM will be used for binary endpoints. The mixed models will include the categorical fixed effects of treatment, visit and treatment-by-visit interaction, and main stratification factor prior bDMARD use. For the MMRM analysis of change from baseline in continuous endpoints, the baseline measurement will be included as a continuous fixed

covariate. The categorical fixed effect of subject's discontinuation status may also be included in the model as appropriate. Unstructured, Toeplitz, compound symmetry, or other covariance structures may be considered.

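### Long-term binary response is planned on As Observed data only, so no summary shows response maintained on study drug

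*SAP*

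**What the plan says.** - **Data basis.** SAP 9.3 states "Analyses will be based on As Observed (AO) data", and AO is the only imputation entry in SAP Table 5.
- **Meaning of AO (SAP 9.1.2).** "The AO analysis will not impute values for missing evaluations". Also: "Regardless of treatment switching or premature discontinuation of study drug, all observed data will be used in the analysis".
- **Second estimate.** SAP 9.3 adds: "In addition, longitudinal analysis will be performed using MMRM or GLMM as described in Section 9.1.2". This covers every endpoint except the corticosteroid-free proportion. SAP 9.1.2 gives its data basis: "The repeated measure analysis will be conducted using mixed model including As Observed measurements at all visits". It then adds an option: "The categorical fixed effect of subject's discontinuation status may also be included in the model as appropriate".
- **Stopping rule.** From Week 24, at least 20% improvement in both TJC and SJC is needed to stay on study drug. SAP 4.2 (Period 2) continues: "Anyone who does not fulfill this criterion at 2 consecutive visits (starting at Week 24) must be discontinued from study drug". On timing: "subjects will have a study visit at Weeks 16, 20, 24, 36, 48".
- **After stopping drug.** Under SAP 4.2 and Protocol 5.1, subjects should keep attending scheduled visits unless they withdraw consent, and the investigator chooses their treatment.
- **Other data rules.** SAP 9.1.2 defines NRI: a subject with a missing value, or at any visit after stopping study drug, is a non-responder. NRI is primary for Period 1 binary endpoints but does not appear in Table 5. The Observed Cases rule, which drops values after discontinuation, is limited to Period 1.
- **Status of the results.** SAP 9.1.1 makes long-term efficacy descriptive, with confidence intervals and no testing.

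**The concern.** The Period 2 objective includes the long-term efficacy of upadacitinib 15 mg and 30 mg. A reader of a Week 260 ACR20 percentage will tend to take it as the share of the arm still responding on the drug. AO does not measure that, for two reasons:

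- A subject who stopped study drug and later improves on another treatment is counted as a responder in the upadacitinib sequence.
- A subject who withdraws or misses the visit leaves the denominator.

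The stopping rule is also tied to the endpoint. ACR20 (SAP 9.4.1) requires at least 20% improvement in both TJC68 and SJC66. A subject stopped under the rule was therefore an ACR20, ACR50 and ACR70 non-responder at both triggering visits. If that subject later withdraws, a known failure on drug drops out of the AO percentage. If the subject stays and does well on something else, the failure becomes a success.

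What is at stake is the description of durability. A flat or rising curve could reflect sustained response, substituted therapy or attrition, and the planned tables would not tell these apart.

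**Working it through.** The documents give no long-term response rate, retention or off-drug share, so there is no planned figure to reproduce. Every rate below is an assumption, shown as a range.

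**Timing.** The rule starts at Week 24 and needs two consecutive visits. The first pair is Weeks 24 and 36, so it first acts at Week 36.

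**Direction.** At a given visit let *a* be the share observed on drug, *b* the share observed off drug and *c* the share missing, with a + b + c = 1. Let p_on, p_off and p_miss be the response rates in these groups.

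- AO = (a·p_on + b·p_off) / (a + b)
- NRI = a·p_on
- Treatment-policy rate = a·p_on + b·p_off + c·p_miss

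Since a + b ≤ 1, AO ≥ a·p_on + b·p_off ≥ NRI. AO therefore cannot fall below NRI. The one exception is ACR response under SAP 9.4.1, where the NRI steps first fill missing components by LOCF and so can turn a missing visit into a response.

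**Size against response maintained on drug.** Assume p_on = 85%, share off drug d = 20–40%, response off drug r = 40–60%, and a fraction s of those off drug still followed. Then AO = [(1−d)·0.85 + d·s·r] / [(1−d) + d·s] and NRI = (1−d)·0.85.

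| d | s | r | AO | NRI | Gap (points) |
|---|---|---|---|---|---|
| 0.2 | 1 | 0.4 | 0.76/1.00 = 76.0% | 68.0% | 8.0 |
| 0.2 | 1 | 0.6 | 0.80/1.00 = 80.0% | 68.0% | 12.0 |
| 0.4 | 1 | 0.4 | 0.67/1.00 = 67.0% | 51.0% | 16.0 |
| 0.4 | 1 | 0.6 | 0.75/1.00 = 75.0% | 51.0% | 24.0 |
| 0.2 | 0.5 | 0.4 | 0.72/0.90 = 80.0% | 68.0% | 12.0 |
| 0.2 | 0.5 | 0.6 | 0.74/0.90 = 82.2% | 68.0% | 14.2 |
| 0.4 | 0.5 | 0.4 | 0.59/0.80 = 73.8% | 51.0% | 22.8 |
| 0.4 | 0.5 | 0.6 | 0.63/0.80 = 78.8% | 51.0% | 27.8 |

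The gap is 8–24 points with the follow-up that the plan asks for (s = 1), and 12–28 points if half are followed.

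**Size against a treatment-policy rate.** With c = 0, AO equals the treatment-policy rate. With missing data, assume p_on = 80%, p_off = 50%, b = 10% and c = 10–30%:

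- If every missing subject is a non-responder: c = 10% gives AO 76.7% against 69.0% (+7.7 points); c = 30% gives 75.7% against 53.0% (+22.7 points).
- If missing subjects respond at 80%: AO is 76.7% against 77.0% (−0.3 points) and 75.7% against 77.0% (−1.3 points).

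**Discontinuation status in the model.** The SAP does not say when this factor enters or how its levels are averaged. Suppose 20% are off drug, with response 80% on drug and 40% off. Weighting by observed proportions gives 0.8×0.80 + 0.2×0.40 = 72%. Equal weights on the logit scale give 62%. The SAP does not specify equal weighting; the example shows only that the reported rate depends on a choice left open, and here the shift is downward.

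**The case against.** **The rule stops drug, not follow-up.** A reader might infer that non-responders are removed from the data from Week 24. The documents do not support that. Subjects off drug should attend all visits, AO keeps their values, and poor results then lower the percentage. The denominator shrinks only through withdrawal or missed visits. Nor can the same subject be lost from the denominator and counted on other therapy at the same visit. The extreme gap of 17–34 points (85% against 68% and 51%) needs every off-drug subject to leave, which is not the planned course. This objection stands, and the full-follow-up rows above are the planned case.

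**AO by randomized sequence is a legitimate treatment-policy summary.** With complete follow-up it has no bias for that quantity. NRI has its own weakness: over 260 weeks it scores stopping for any reason as non-response and so mixes retention with efficacy. This also stands, and is the reason to show both summaries. The SAP names no long-term estimand.

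**The longitudinal models help.** SAP 11.1 presents them as an additional sensitivity analysis. The rule depends on recorded joint counts, so if stopped subjects leave, a missing-at-random likelihood model uses their earlier poor values. That partly answers the denominator concern. It does not separate response on upadacitinib from response on other therapy, because the model includes off-drug values.

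**Some information is already planned.** Binary tables give frequencies, SAP 7.0 tabulates Period 2 discontinuation with reasons, and Appendix B counts COVID-19-affected visits. None of these splits each visit's contributors into on drug and off drug.

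**Conclusion.** The gap in the plan is real: AO is the only data basis for long-term binary response, and no summary isolates response maintained on study drug. Relative to that quantity AO is too high, by about 8–24 points with full follow-up and 12–28 points with half followed. The sizes rest on assumed inputs of 85% on-drug response, 20–40% off drug and 40–60% response off drug. The direction holds without them, apart from the LOCF exception for ACR.

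A reader might go further and conclude that the AO percentages overstate durable response as such. That follows only if durable response means response while on drug, a meaning the SAP does not adopt. Against a treatment-policy rate the bias may be nil, slightly negative or large and positive, depending on subjects whose outcomes are unknown.

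The consequence is confined to descriptive Period 2 reporting. Period 1 inference is unaffected; SAP 11.1 states that its reporting is complete and that this version governs only future long-term analyses.

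**What to change.** - Keep AO and label it a treatment-policy description.
- Beside it, add an NRI summary for the key binary endpoints in the Table 5 footnote: ACR20/50/70, LDA and CR by DAS28(CRP) and by CDAI, and Boolean remission. Use the SAP 9.1.2 rule (non-responder after study drug discontinuation and at missing visits) and state that the SAP 9.4.1 LOCF step for ACR components does not apply to long-term visits.
- Show visits missed for COVID-19 logistics as a separate count. The SAP defines no rule for imputing long-term binary response at such visits.
- By visit and sequence, print the numbers observed on drug, observed off drug and missing.
- Fit the long-term GLMM and MMRM without discontinuation status. If it is included, average over its levels by their observed proportions.

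The cost is small: a further NRI summary for the key endpoints, a by-visit count and a few sentences in SAP 9.1.2 and 9.3, with no new data collection. The downside is that the NRI figures will look less favourable and combine retention with response, which a footnote should say.

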**Table 5. Summary of Efficacy Variables and Corresponding Analyses for Long-Term Efficacy Analysis**

Efficacy Variables	Analysis Method
Binary Endpoints:	

 
• ACR20/50/70 response by visit
 
• LDA and CR based on DAS28(CRP), DAS28 (ESR), SDAI, and CDAI criteria by visit
 
• Proportion of subjects with change from baseline in HAQ-DI <math>\leq -0.3</math> and <math>\leq -0.22</math>, respectively
 
• Boolean remission
 
• Proportion of subjects with no concomitant corticosteroid use (among subjects with corticosteroid use at baseline)*
 
	
 
• Point estimate and 95% CI of the response rate for each randomized treatment group sequence
 
• Point estimate and 95% CI of the response rate using GLMM model for each randomized treatment group sequence (*endpoint excluded from this analysis)
 
• Plot for each randomized treatment group sequence over time for key endpoints#
 
• Imputation: AO
 
• Analysis Set: FAS
 

Continuous Endpoints:	

 
• Change from baseline in individual ACR components by visit
 
• Change from baseline in DAS28 (CRP) and DAS28 (ESR) by visit
 
• Change from baseline in CDAI and SDAI by visit
 
• Change from baseline in morning stiffness (severity and duration) by visit
 
• Change from baseline in EQ-5D-5L by visit
 
• Change from baseline in FACIT-F
 
• Change from baseline in RA-WIS
 
• Change from baseline in SF-36 by visit
 
	
 
• Point estimate and 95% CI of mean change from baseline together with SD, for each randomized treatment group sequence
 
• Point estimate and 95% CI of change from baseline using MMRM model for each randomized treatment group sequence
 
• Plot for each randomized treatment group sequence over time for key endpoints#
 
• Imputation: AO
 
• Analysis Set: FAS
 

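### The long-term response-rate intervals (normal approximation and GLMM) break down in any sequence-by-visit cell with 0% or 100% responders, and the SAP has no rule for such cells

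*SAP*

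**What the plan says.** SAP 9.3 analyses the main long-term endpoints "at Week 1, 2, 4, 8, 12, 16, 20, 24, 36, 48, every 12 weeks through Week 240, and Week 260", by randomised treatment sequence. SAP 9.1.1 defines four sequences and keeps the two placebo-first groups apart.

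Two intervals are planned for the same response rates:

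- **Descriptive.** SAP 9.3 asks for "frequencies and percentages with 95% CI using normal approximation for binary endpoints".
- **Model-based.** SAP 9.3 adds that "longitudinal analysis will be performed using MMRM or GLMM as described in Section 9.1.2 for all endpoints", with one exception given below. SAP 9.1.2 says "GLMM will be used for binary endpoints" and "The mixed models will include the categorical fixed effects of treatment, visit and treatment-by-visit interaction", plus prior bDMARD use. Table 5 asks for "Point estimate and 95% CI of the response rate using GLMM model for each randomized treatment group sequence".

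One endpoint is left out of the model. SAP 9.3 applies it "for all endpoints except proportion of subjects with no concomitant corticosteroid use", and Table 5 repeats the exclusion.

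SAP 9.1.2 leaves open the covariance structure and an optional effect for discontinuation status. It does not name the link, the estimator or the interval method, and it has no provision for a cell in which nobody, or everybody, responds.

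**The concern.** A categorical treatment-by-visit term gives every sequence-by-visit cell its own parameter. If a cell has no responders, its log-odds has no finite maximum likelihood estimate. The normal-approximation interval fails in the opposite direction, because its estimated standard error is zero. The report could then show, for one cell, a descriptive interval of 0-0% and a model interval of 0-100%, and neither describes the uncertainty.

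Six of the 14 modelled endpoints are stringent: ACR70, clinical remission on four indices, and Boolean remission. They are the ones most likely to have empty cells at the first visits, in the two placebo-first sequences of 100 planned subjects each. At stake are the printed error bars for those cells, and the risk of an unplanned choice of model once the output is seen.

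**Working it through.** **1. The plan's own figures.** The documents give no figure for the long-term model. The only response rates are the Week 12 design assumptions in SAP 4.3: placebo 37% for ACR20 and 15% for LDA, with differences of 21 and 22 points. Using pooled variance, two-sided 0.025 and 200 less 10% = 180 per group, power is 96.3% for ACR20 and 99.5% for LDA, consistent with the stated 90% or more. These rates do not produce empty cells: 0.85^100 is below 1 in 10 million.

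**2. Number of cells.** There are 10 visits up to Week 48, 16 from Week 60 to Week 240 ((240 - 60)/12 + 1), and Week 260, making 27. Four sequences give 4 x 27 = 108 cells per endpoint. Table 5 lists 3 ACR levels, 8 LDA/CR definitions, 2 HAQ-DI cut-offs, Boolean remission and corticosteroid use: 15 in all, of which 14 are modelled.

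**3. Descriptive interval.** The formula is p +/- 1.96 sqrt(p(1 - p)/n). With p = 0 or p = 1 the second term is 0.

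- 0/100: normal approximation 0-0%. Wilson upper limit = 1.96^2/(100 + 1.96^2) = 3.84/103.84 = 3.7%. Clopper-Pearson upper limit: 3.6%.
- 0/200: normal approximation 0-0%. Wilson upper limit = 3.84/203.84 = 1.9%.

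Coverage at n = 100 for very low true rates is close to 1 - P(0 responders). One responder already gives 1% +/- 1.96 sqrt(0.01 x 0.99/100) = 1% +/- 1.95 points, which covers both rates below, and counts high enough to miss on the other side are very rare.

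- True rate 0.5%: 1 - 0.606 = 39%.
- True rate 1%: 1 - 0.366 = 63%.

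**4. Model interval.** Data were simulated for 200/200/100/100 subjects and five visits, with a separate parameter for each sequence-by-visit cell, prior bDMARD use, a logit link and one empty cell (0/100).

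- *Fixed-effects logistic fit.* The cell estimate and SE were -11.6 and 20 after 10 iterations, and -21.6 and 2,923 after 20. The Wald interval was 0-100% both times. Stopped at 5 iterations, the fit gave -6.6 and an interval of 0.01-3.3%, so the stopping rule sets the answer.
- *Random-intercept GLMM.* With the cell parameter fixed at -4, -8, -12 and -20, the profile log-likelihood was -1037.23, -1031.83, -1031.688 and -1031.6851. It keeps rising, so there is no finite maximum. The interval was 0-6% at -8, 0-98% at -10 and 0-100% from -12 on. The unconstrained fit stopped at about -35 without convergence.
- *Marginal (GEE) fit.* No estimate was returned.
- *Effect on other cells.* In a separate random-intercept fit with three empty Week 1 cells, the optimiser converged. The empty cells had SEs of 260-335 and all others 0.19-0.83. Refitting without the empty cells gave the same log-likelihood (-909.7996) and the same other estimates to two decimals. The reason is that an empty cell's likelihood contribution tends to 1.

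**5. Chance of an empty cell.** The Week 1 placebo rate for a stringent endpoint is an assumption, so a range is shown. P(empty) = (1 - p)^n. The two placebo-first sequences contain different subjects, so for one visit P(at least one empty) = 1 - (1 - P(empty))^2.

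| Assumed true rate | One sequence of 100 empty | At least one of two empty | One sequence of 200 empty |
|---|---|---|---|
| 0.5% | 61% | 84% | 37% |
| 1% | 37% | 60% | 13% |
| 2% | 13% | 25% | 1.8% |
| 5% | 0.6% | 1.2% | below 0.1% |

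**The case against.** The strongest reply is that little depends on these cells. SAP 9.1.1 plans no testing in the long-term analysis, SAP 11.1 calls the longitudinal models an additional sensitivity analysis, and Period 1 reporting is complete. That stands, and it keeps the severity low.

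A second reply is that empty cells are not shown to occur. That also stands as a limit. Entry requires 6 swollen and 6 tender joints on 66/68 counts, whereas the remission definitions use 28-joint counts. No minimum DAS28 or CDAI is required, and SAP 6.1 provides for baseline DAS28 of 5.1 or less. At an assumed rate of 5% the problem almost disappears.

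A reader might also infer four stronger things that the documents do not support:

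- **That the whole GLMM fails.** In the random-intercept model the other cells are unaffected. Non-convergence depends on software and on choices that the SAP leaves open.
- **That the COVID-19 analysis is undermined.** Appendix B retains the GLMM for pandemic-related missing data, but it also says that all subjects were then in Period 2. Those gaps are not in the Week 1-2 cells.
- **That every binary endpoint is modelled.** The corticosteroid endpoint is excluded.
- **That the chance of an empty cell can be multiplied over Weeks 1 and 2.** The same subjects are seen at both visits, so only single-visit figures are given here.

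None of this answers the algebra: a 0/n cell still gets a 0-0% descriptive interval, and no stated rule covers the model estimate.

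**Conclusion.** The error bars are wrong as written for any cell with 0% or 100% responders. The descriptive part is certain whenever such a cell occurs, applies to all 15 binary endpoints, and needs no modelling assumption. The GLMM part applies to 14 endpoints and assumes unpenalised maximum likelihood, a logit link and Wald limits, none of which the SAP names.

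How often it happens rests on assumed early rates. It is likely at true rates of about 1% or less, and unlikely at 5%. The same algebra applies to a cell in which everyone responds, but the documents give neither late response rates nor late numbers, so no frequency is claimed there. The effect is limited to the affected cells of a descriptive and sensitivity analysis. Week 12 primary and key secondary conclusions do not change. Severity: minor.

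**What to change.** 1. In SAP 9.3 and Table 5, replace the normal-approximation interval for long-term response rates with the Wilson interval.
2. In SAP 9.1.2, keep all visits in the GLMM. Add that any sequence-by-visit cell with 0% or 100% responders is taken out of the model, with its parameter, and reported as the observed proportion with its Wilson interval. In the random-intercept check this left the other estimates unchanged.

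Do not solve the problem by starting the model at Week 24. That would drop anyone lost before then and discard early responses that inform later missing values, which weakens the missing-at-random argument in Appendix B. The Period 1 analysis is not a like-for-like replacement for Weeks 1-12, because it combines the two placebo groups.

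The cost is a few sentences of SAP text and standard software options. The downside is slightly asymmetric intervals and no model-based estimate for the affected cells.
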